1.3.1.2 Cytokine Activation and Neonatal Post-CPB Inflammation

CPB results in myocardial ischemia/reperfusion. This in turn causes oxidative stress and the formation of reactive oxygen species (ROS). The immature myocardium seems more vulnerable to oxidative stress than adult myocardium, and the degree of pre-existing cyanosis may significantly contribute to the ROS mediated myocardial dysfunction⁵⁰⁻⁵². Oxidative stress precedes the release of cytokines during congenital cardiac surgery, indicating that ROS may be important initiators of a biological cascade that can culminate in myocardial dysfunction and low cardiac output^{50, 53, 54}. Hemolysis, presumably from the CPB circuit and measured by plasma free hemoglobin levels, was recently indicated to be an especially important marker in predicting post-CPB clinical course, perhaps through its potent oxidative effects⁵⁴.

In general terms, cytokines are produced by multiple cell types, including cardiac myocytes and fibroblasts, and bind to receptors on multiple cell types, activating transcription factors such as nuclear factor kappaB (NFkB) and AP-1⁵⁵⁻⁵⁸. Cytokines released in the context of ischemia/reperfusion and oxidative stress include tumor necrosis factor alpha (TNF α) and the interleukins (ILs) IL-2, IL-6, IL-8, and IL-10^{4, 7, 15-18, 30, 50, 51, 53, 54, 59-71}. TNF α has been clearly demonstrated to be released during cardiac surgery and CPB. Through binding to transmembrane receptors, it causes the activation of several transcription factors – notably NFkB^{57, 58}. IL-2, IL-6 and IL-8 are pro-inflammatory cytokines that mediate the activation and maturation of inflammatory cells and thereby the augment release of ROS and proteases beyond that initiated by the original ischemia-reperfusion insult^{3, 62-64, 72}. IL-1 β is also pro-inflammatory, potently recruiting inflammatory cells and inducing proteases^{3, 73, 74}. IL-1 β forms another potent pathway for NFkB formation has been reported following congenital heart surgery^{60, 61, 75, 76}. However, the overall impact of this potent cytokine to downstream effector systems remains to be established. Chemokines (eg - MCP-1) augment the egress and maturation of inflammatory cells, such as neutrophils, into the myocardium and thereby facilitate cytokine activation^{77, 78}. In contrast to the pro-inflammatory ILs, anti-inflammatory cytokines, such as IL-10, appear to inhibit further cytokine release from multiple cell types^{3, 79}. The balance of pro- and anti-inflammatory cytokines is believed to determine the degree of inflammatory response. It is clear that a wide array of molecules play a role in the post-CPB response, but equally clear that our understanding of these roles can only be derived from further clinical studies.

Modified ultrafiltration (MUF) is commonly employed at the conclusion of CPB in order to reduce the impact of hemodilution^{17, 60, 71, 72, 75, 76, 80, 81}. MUF has been shown to transiently affect cytokine levels, but cytokine activation continues unabated in the early post-operative period⁸¹. Moreover, TNF and IL-8 levels appear to be relatively unaffected by MUF, whereas IL-10 levels are reduced - potentially contributing to a 'feed-forward' cytokine activation process in the early post-CPB period^{4, 57, 60}.

1.3.1.3 The cytokine response of neonates in general is known to be qualitatively and quantitatively distinctive in comparison to older infants.

A small number of studies have specifically examined the neonatal cytokine response to CPB as distinguished from older infants and pediatric patients^{8, 16-18, 71}. In general, investigators have uniformly noted augmentation of IL-10 levels when measured and variability of IL-6, IL-8, and TNF alpha responses. Preoperative glucocorticoid administration in children²⁹ and

hypothermia on bypass¹⁹ augment these profiles, while intraoperative PGE1 administration in adults on CPB result in similar cytokine profiles⁸². In summary, there is increased IL-10 with high variation in reported pro-inflammatory cytokine levels in neonates, and common practices in neonatal preoperative or intraoperative care may influence these balances.

1.3.1.4 Matrix Metalloproteinases (MMPs) and Neonatal Post-CPB Inflammation

MMPs are a family of at least 25 zinc-dependent proteins that were classically associated with their ability to degrade collagens or other extracellular matrix macromolecules. These properties are important features of MMP function, but intensive investigation has revealed much broader roles for these proteins in the myocardium and in other tissues. MMP degradation products of collagens and other macromolecules often have significant biological activities, and MMPs also mediate the activity of many biologically important growth factors (e.g., IGF family members, TGF β family members^{83, 84}). MMPs have become a very active arena of investigation in the adult heart. MMPs have been recognized to increase in the bronchoalveolar lavage fluid of pediatric patients, including neonates, with lung disease⁸⁵⁻⁸⁷. Serum MMP levels have been altered in premature infants with bronchopulmonary dysplasia or interventricular hemorrhage⁸⁵, and increased MMP-3 (stromelysin-1) was found in the non-necrotic gut of infants with necrotizing enterocolitis⁸⁸. Altogether, however, few studies of MMP levels have been performed in the neonatal population or the immature heart.

Two reports have found elevation of MMP-2 in the heart after asphyxia-induced cardiac ischemia in piglets, with no changes in MMP-9^{52, 89}. There are currently no clinical data for neonates, infants, or older children to predict the nature of the MMP response post CPB. However, Cheung et al. studied neonates on ECMO and were able to show that plasma MMP-2 was elevated in a time-dependent fashion, but not MMP-9⁹⁰, and the adult data suggest MMP changes are important in the response to a variety of cardiac stresses and injuries. Induction of MMPs has been found in patients following myocardial infarction, in ischemia/reperfusion, and most importantly in the context of cardiac surgery^{77, 78, 91-99}. Importantly, a cause-effect relation between MMP induction and changes in myocardial structure and function has also been demonstrated in the context of ischemia/reperfusion⁹⁹⁻¹⁰². However, a quantitative assessment of MMP profiles in congenital cardiac surgery and the inter-relationship to postoperative clinical status and cytokine activation has not been performed.

The present study will examine a cassette of MMP types corresponding to three important soluble MMP classes: the interstitial collagenases (MMP-1,-8,-13), gelatinases (MMP-2,-9) and matrilysin/stromelysin (MMP-3,) using a multiplexer approach which has been optimized, validated and calibrated for each of these MMP species. As published reports describe an apparent cell and stimulus-specific effect of PGE1 on production of MMPs¹⁰³, the net effect of PGE1 administration as a confounding variable on total circulating MMP levels in neonates pre- and post-CPB is difficult to predict. It is likely that the effects on augmentation or suppression of individual MMPs in this setting will be tissue specific. Our study will provide the initial clinical data for further investigation of this topic.

1.3.2 Microribonucleic acid

Microribonucleic acid (miRNAs) are a recently discovered small, non-coding RNAs that regulate protein levels post-transcriptionally¹⁰⁴. miRNAs play important regulatory roles in many cellular processes, including differentiation, neoplastic transformation, apoptosis and cell replication and regeneration. Given these regulatory roles, it is not surprising that miRNA expression has been implicated in numerous disease states. Recent studies have reported significant levels of miRNAs in serum and other body fluids, raising the possibility that circulating miRNAs could serve as useful clinical biomarkers. Even more interesting, given their control over multiple effectors of complex intracellular pathways make miRNAs tremendously attractive as therapeutic targets, distinguishing them from single protein targets (i.e. enzyme or receptor) of most conventional drugs¹⁰⁵. Various biochemical means of stabilizing and delivering miRNAs antagonists have already proven successful. miRNAs role in cardiovascular disease is still incompletely understood and under investigation¹⁰⁶.

1.3.3 Assessment of Inflammatory Markers

Until recently, studying markers for all of these processes has been a practical impossibility in neonates due to the volume of blood sampling needed and the specialized nature of the measurements. However, recent technical advances included in this application make it realistic to match clinical outcomes with the time course of a broad array of serum pro-and anti-inflammatory cytokines, MMPs, myeloperoxidase and miRNAs. These molecules, known as analytes can all be measured from the same small blood sample by a process called multiplexing. The multiplex analysis technology in this proposal was developed commercially by Luminex Corporation and combines the sensitivity of enzyme-linked immunosorbent assays with the specificity and multiplexing capability of flow cytometric detection. The equipment described in this proposal enables up to hundreds of different analytes to be measured within a single sample of less than 50 microliters of plasma. For the purposes of this proposal we will measure the more selected panel of MMPs, cytokines and miRNAs detailed in Appendix 2.

1.4 Rationale (for study population)

The study will focus on neonates for a few reasons. Although their post- CPB clinical course is typically more severe and ICU care more prolonged than older children, their modes of morbidity are also well characterized. Further, the high level of severity itself provides a substrate for identifying the positive effects of a particular therapy. Finally, a therapy identified as beneficial has the greatest potential for benefit in this vulnerable population.

The primary impediment to performing mechanistically based controlled studies in the area of congenital heart surgery is the complexity and diversity of the lesions and ages that confront the pediatric cardiologist and surgeon. However, the conditions that require neonatal cardiac surgical intervention are all relatively severe, and the responses of neonates to cardiopulmonary bypass (CPB) are relatively uniform and well defined. Further, the volume of neonates undergoing CPB is quite large, providing adequate sample size to test a focused intervention and set of hypotheses. The reductionist approach of this project in regards to the complexity of the congenital heart malformations and surgical procedures has been chosen to balance the objectives of scientific rigor, acceptable volume and clinically meaningful endpoints. It is recognized that a large number of patients are not being considered in this initial proposal, such

as infants and older children, where it is also likely that post bypass injury is an important problem. However, inclusion of only the neonatal subset of patients will decrease the complexity of the study design, allowing for a sharp and mechanistic focus.

1.5 Known and Potential Risks and Benefits

1.5.1 Risk of Study Procedures

The surgery and post-operative recovery to discharge will follow standard facility SOPs and be based upon the decision of the primary physician caring for the neonate.

Risks related to the study include:

- Risk of Methylprednisolone administration:

The possible risks or discomforts of the study are minimal. Intravenous steroids are widely used for a myriad of inflammatory conditions including cardiopulmonary bypass. When steroid treatments are given for repeated doses, they may cause important disturbances in the stomach or intestine (e.g. ulcers), pancreas, salts and sugar in the blood, or the ability to fight infection.

- Risk of Infection due to Sampling:

This risk is quite small. The risks associated with blood collection are minimal since an arterial and venous catheter will be in place for routine clinical use. Thus, any risks associated with a second venipuncture are eliminated. The volume of blood drawn for these studies has been carefully considered to minimize the potential risk of reducing circulatory volumes in the post-operative period. The risk associated with the intra-operative samples is minimal since volume supplementation occurs during this period as a matter of course for the conduct of cardiopulmonary bypass. The blood samples at later time points have been carefully considered and have been spread over a 30-hour period. It is standard of care to use a urine catheter and the risk of acquiring an infection resulting from urine collection is minimal.

- Risk of Developmental Testing

The evaluation performed by the developmental specialist at one year of age does not involve any invasive testing. This portion of the study will take approximately one hour of time. There are no risks associated with this evaluation.

- Risk of loss of confidentiality:

The risks with hemodynamic and postoperative data do not constitute health risks, but rather those of data security and confidentiality. Confidentiality will be maintained by making the study data available to only the investigators, and by omitting specific patient information (name, hospital number) from any published data.

- Protection against Risk:

All parent(s)/legally authorized representatives (LAR), (their families and their personal physicians where appropriate), will be informed in advance of executing the informed consent document of all potential risks attendant to participation in study protocol as described above. Throughout the performance of this study and during the performance of all procedures, subjects will be carefully monitored in accordance with current medical practices. Treatment with a single

dose of MP as proposed in this study has had few if any reported side effects. Patients whose parent(s)/legally authorized representatives (LAR) refuse consent or who are not enrolled in this study may receive intraoperative MP, based on their attending cardiothoracic surgeons or anesthesiologist preference. Based upon the extensive experience with all aspects of the study protocol procedures, it is anticipated that the risk of adverse events associated with the study will be acceptably low. Maximum efforts will be undertaken to ensure the safety of all study participants. All personnel involved in performance of the study and its procedures will be fully trained and extensively experienced. All serious adverse events will be required to be reported to the local IRB per local protocol within 24 hours of it being brought to the attention of the attending physician of the patient as well as the principal investigator of the study. Other (non severe) adverse events will be reported according to local IRB protocol. In accordance with the current revision of the Declaration of Helsinki and other applicable regulations, a patient (or patient's parent(s)/legally authorized representatives (LAR)) has the right to withdraw the patient from the study at any time and for any reason without prejudice to patient's future medical care by the physician or at the institution. Should a patient (or patient's parent(s)/legally authorized representatives (LAR)) request or decide to withdraw from the study, all efforts will be made to complete and report the observations as thoroughly as possible through the date of withdrawal and the protocol-related observations for the last visit. If the patient is withdrawn due to an adverse event, the Investigator is to arrange for the patient to have follow-up visits until the adverse event has resolved or stabilized in addition to the evaluations required for the end of the study. Confidentiality will be maintained by making the study data available to only the investigators, and by omitting specific patient information (name, hospital number) from any published data. Appropriate HIPAA consents and procedures will also be employed to ensure confidentiality.

1.5.2 Benefits

There is no known, direct benefit to participation. Neurodevelopmental testing at 1 year of age is not standard of care at all institutions, but is a secondary endpoint in this study. Many families would consider this evaluation by a developmental specialist at a year of age a benefit.

2 AIMS

2.1 Primary Aim

- Compare the effects of intraoperative methylprednisolone (MP) to placebo on morbidity and mortality following neonatal cardiopulmonary bypass (CPB).

2.2 Secondary Aims

- Compare the effects of MP to placebo on the duration of mechanical ventilation, ICU and hospital stay post cardiac surgery.
Hypothesis: Neonates receiving MP will have decreased morbidity and capillary leak which will result in shorter ICU and hospital stay.
Endpoints:
Time of mechanical ventilation, ICU stay, and total hospital stay
Number of days alive and out of the hospital at 90 days post cardiac surgery
- Compare the effects of MP to placebo on neurologic and developmental outcomes at 1 year.
Hypothesis: Neonates receiving MP will have improved neurologic and developmental outcomes at 1 year.
Endpoints: Bayley Scale of Infant Development at 1 year
- Compare the effects of MP to placebo on the inflammatory response to cardiopulmonary bypass.
Hypothesis: Neonates treated with MP will have altered production of inflammatory cytokines and other biomarkers of organ dysfunction.
Endpoints:
 - Multiple agents serially measured preoperatively and following CPB by novel multiplexer technique including but not limited to:
 - Cytokines
 - Matrix metalloproteinases (MMPs)
 - Microribonucleic acid (miRNAs)
 - Endothelial function
- Compare the safety of MP to placebo following cardiac surgery.
Hypothesis: Neonates treated with MP will have a similar rate of adverse events over the first 30 days after surgery.
Endpoint:
 - Incidence of adverse events and serious adverse events
 - Rise in creatinine and incidence of acute kidney injury

3 SELECTION OF PARTICIPANTS

3.1 Inclusion Criteria

- \leq 1 month of age (\leq 31 days of life)
- Male and female patients
- Scheduled to undergo cardiac surgery involving CPB
- Consent obtained from parent(s)/Legally Authorized Representative (LAR)

3.2 Exclusion Criteria

Patients who meet any of these criteria are not eligible for enrollment as study participants

- Prematurity: < 37 weeks post gestational age at time of surgery
- Treatment with intravenous steroids within the two days prior to scheduled surgery.
- Participation in research studies involving the evaluation of investigational drugs or vaccines within 30 days of randomization.
- Suspected infection that would contraindicate steroid use (e.g. – Herpes)
- Known hypersensitivity to IVMP or one of its components or other contraindication to steroid therapy (e.g. - gastrointestinal bleeding).
- Preoperative use of mechanical circulatory support or active resuscitation at the time of proposed randomization.
- Inability to comply with study procedures.

4 Study Design

This is a multi-center, prospective, randomized, double blind, placebo controlled study of intraoperative MP in neonates undergoing CPB. Patients will be allocated to one of the 2 study groups in the ratio of 1:1. The randomization will be stratified by corrective vs. palliative surgery and by surgeon. The Primary Endpoint is a composite morbidity-mortality outcome, evaluated as intention to treat (ITT). Secondary endpoints include inotropic score, incidence of LCOS, fluid balance, ICU stay parameters, levels of inflammatory markers, safety parameters, and neurodevelopmental outcomes at 1 year. A two-sided test with a type I error rate of 0.05 will be used for all endpoints with no adjustments of the p-value for multiple testing.

It is expected that 190 patients (95 patients per treatment arm) will be needed to be enrolled in the study to show a significant difference between groups. The annual amount of eligible & consenting patients at MUSC for this trial and a similar trial over 3 years was 35 cases/year. The annual amount of eligible patients at Children's Healthcare of Atlanta based on the surgical volume in 2012 would be 74 neonates. Anticipating a 70% consent rate would result in 50 cases a year. As such, this study would expect to reach the goal of 190 evaluable subjects in 4 years, within the 5 year proposed grant cycle.

4.1 Study Endpoints

4.1.1 Primary Endpoint

Composite Morbidity-Mortality Outcome

The composite morbidity-mortality outcome will be met if any of the following occur after surgery but before hospital discharge: death, cardiac arrest, extracorporeal membrane oxygenation, renal insufficiency (creatinine more than two times normal), hepatic insufficiency (aspartate aminotransferase or alanine aminotransferase more than two times normal > 36 hrs post-op), or lactic acidosis (>5mmol/L, that is increasing). This outcome is ideal because death rarely occurs in this population. Similar to others^{107,114,115}, we have found this endpoint to be highly associated with other important clinical outcomes in this population (Table 1).¹¹⁷

4.1.2 Secondary Endpoint

Compare the effects of MP to placebo on inotropic requirements, incidence of low cardiac output syndrome and fluid balance over the first 36 hours after surgery.

Compare the effects of MP to placebo on the duration of mechanical ventilation, ICU and hospital stay post cardiac surgery; and number of days alive and out of the hospital 90 days post cardiac surgery.

Compare the effects of MP to placebo on neurologic and developmental outcomes at 1 year.

Compare the effects of MP to placebo on the inflammatory response to cardiopulmonary bypass.

Compare the safety of MP to placebo following cardiac surgery.

5 STUDY TREATMENT REGIMEN

5.1 Premature Study Discontinuation

5.1.1 Premature Discontinuation of Study Treatment

Study treatment may be prematurely discontinued for any participant for any of the following reasons:

1. Study participation will be discontinued if a participant:
 - a. Does not undergo cardiac surgery using cardiopulmonary bypass.
2. Study treatment may also be prematurely discontinued for any participant if the investigator or attending physician believes that the study treatment is no longer in the best interest of the participant.
3. Participants will be analyzed in the following groups
 - a. Modified ITT sample – all randomized participants who underwent CPB.
 - b. Safety sample – all randomized participants who underwent CPB and received study drug.
 - c. Per protocol sample – All randomized participants who underwent CPB, received study drug, and had no major protocol deviations (i.e. open label steroids).

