7.1.4 Intraoperative Management

Study drug will be delivered to the operating room with the patient. The anesthesiologist will infuse the study drug intravenously over 30 minutes after central lines are placed and study labs have been drawn. The study drug will be started prior to skin incision. Intraoperative management, surgical and bypass techniques will not be standardized, but will be recorded in the CRFs.

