8 STUDY DRUG PREPARATION AND ADMINISTRATION

Study medication will be purchased, stored and tracked by Investigational Drug Services. When a patient is identified as eligible for the study and the parent(s)/LAR have given informed consent, the physician will provide an order to the investigational pharmacist. The investigational pharmacist will then assign the patient to the next available Subject ID on the corresponding list based on information on the surgeon and the surgery type, and prepare the study drug according to the treatment name provided on the randomization list.

Study medication:

Methylprednisolone: will be given at a dose of 30 mg/kg body weight and a concentration of 62.5 mg/cc mixed in a 3 mL syringe.

Placebo: Normal saline will be drawn up in an identical volume to that needed for active study drug.

The pharmacy will label the study medication with the special instructions to read:

“Send dose with patient to the OR to be administered IV over 30 minutes after central lines are placed and blood is drawn. Follow infusion with 3 mL Normal Saline Flush.”

The study drug will be delivered in a blinded fashion to the anesthesiologist. The study drug will be administered intravenously over 30 minutes with the induction of anesthesia, after central lines have been placed and blood drawn, but prior to skin incision. The infusion will be followed by a 3 mL normal saline flush.

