10.1.2 Serious Adverse Event

An SAE is defined as “any adverse event that suggests a significant hazard, contraindication, side effect, or precaution.” The nature of the disease being study lends itself to a high morbidity and mortality rate. For this reason, SAEs will be collected within the database. Data collection will include events as:

- Death

Any death within the first year of life will be reported as an SAE. SAEs will be reported to the site PI and the study PI within 24 hours of discovering the event. All SAEs will be reported to the IRB within 72 hours of the PIs knowledge of the event. All SAEs will be reported to the local IRB/ DSMB chair within 72 hours of the PI’s knowledge of the event.

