10.2 Collection and Reporting of Events

10.2.1 Collection Procedure

Adverse events will be collected from the time the participant received study drug until the time the event is resolved or until 30 days after the participant completes study procedures, whichever comes first. Adverse events may be discovered through any of these methods:

- Observing the participant.
- Questioning the participant family; this should be done in an objective manner.
- Receiving an unsolicited complaint from the participant.
- An abnormal value or result from a clinical or laboratory evaluation (e.g., a radiograph, an ultrasound, or an electrocardiogram) can also indicate an adverse event.

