12.4 Statistical Methods

Descriptive statistics will be used to characterize the two treatment groups with respect to demographics and baseline clinical characteristics. T-tests, chi-square tests, and non-parametric statistical tests will be used, as appropriate, to compare the groups at baseline. Any significant imbalances will be accounted for in the analyses using multivariable techniques. The primary intention-to-treat analysis comparing the composite outcome between treatment groups will be conducted using generalized linear model. The primary analysis will be adjusted for underlying diagnosis and surgeon. Logistic regression models will be used for the per-protocol analysis and for analyses of secondary categorical outcomes. For continuous variables such as change from baseline in vital signs, hematology, and clinical chemistry parameters, analysis of covariance (ANCOVA) will be utilized with the baseline value used as covariates. Unless otherwise stated, baseline is defined as the last observation before the administration of the study drug. Time to event data (duration of mechanical ventilation, length of ICU stay, and length of hospitalization) will be assessed via non-parametric log-rank tests.

Once half of the study subjects have been recruited and assessed, an interim analysis will also be conducted and presented to the DSMC, for which the p-value thresholds for stopping the study for superiority or futility will be 0.003 and 0.72, respectively. The p-value used at the end of the study with full enrollment will be 0.049, preserving an experiment-wise 2-sided alpha level of 0.05. These stopping thresholds are based on an O'Brien-Fleming alpha spending function. All analyses will be conducted in SAS v9.2 (Cary, NC).

Multiple correlation analyses will be performed between the inflammatory markers and other continuous outcome measures, such as fluid balance, inotropic score and hemodynamic variables. An assessment will also be made of the association between the inflammatory markers and categorical variables, such as the composite morbidity-mortality outcome and its components. Analyzed safety variables will include all reported adverse events, the incidence of acute renal injury and postoperative creatinine, hyperglycemia and infection. All patients who are randomized, received study drug, and underwent cardiopulmonary bypass will be included in the safety analyses.

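### The safety sample requires bypass, which comes after dosing, so infants who are dosed but never reach bypass drop out of the MP-versus-placebo safety comparison

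*Combined protocol and SAP*

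**What the plan says.** Three parts of the plan bear on this point.

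**Who is in the safety analysis.** Section 5.1.1 defines the safety sample as "all randomized participants who underwent CPB and received study drug". Section 12.4 agrees: "All patients who are randomized, received study drug, and underwent cardiopulmonary bypass will be included in the safety analyses". The modified ITT and per-protocol samples in 5.1.1 also require bypass.

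**When exposure happens.** Section 7.1.4 states: "The study drug will be started prior to skin incision". Section 8 has the drug "administered intravenously over 30 minutes with the induction of anesthesia, after central lines have been placed and blood drawn, but prior to skin incision". Exposure therefore comes before bypass in every infant treated according to the protocol.

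**What is collected, and for how long.** Section 10.2.1 states: "Adverse events will be collected from the time the participant received study drug". Section 10.1.2 adds: "Any death within the first year of life will be reported as an SAE". Section 5.1.1, however, says "Study participation will be discontinued if a participant" meets one condition: "Does not undergo cardiac surgery using cardiopulmonary bypass". It makes no exception for an infant who has already been dosed.

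**The concern.** A safety population is normally fixed by exposure. Here it is also fixed by an event that follows exposure and that an acute harm could prevent. An infant who is dosed and then deteriorates or dies before bypass is excluded. So is a dosed infant whose operation is called off or done without bypass. If the drug or its infusion caused the early harm, the safety table would show none of the cases in which that harm stopped bypass, whatever their true number.

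Safety is a stated secondary aim (section 2.2), with a hypothesis of similar adverse-event rates in the two arms. A claim of similarity is weaker when some exposed infants are missing by rule.

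**Working it through.** The plan states no figure on this point, so there is none to reproduce. The check compares the text of the sections and then sizes the gap under stated assumptions.

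**Step 1. Follow a dosed infant who does not reach bypass.**

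| Question | Section | Answer |
|---|---|---|
| Exposed? | 7.1.4, 8 | Yes, the infusion starts before incision |
| Adverse events collected? | 10.2.1 | Yes, from receipt of drug |
| Death in the first year reported? | 10.1.2, 10.2.4 | Yes, with no bypass condition |
| Participation continues? | 5.1.1 | No |
| Follow-up if withdrawn for an adverse event? | 1.5.1 | Yes, until the event settles |
| In the safety sample? | 5.1.1, 12.4 | No |

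The infant's events can be recorded and reported, but no text places the infant in the between-arm safety comparison.

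**Step 2. Check whether another section closes the gap.** Section 12.9 defines an ITT population of everyone randomized, without a bypass condition. It does so for the primary endpoint only, and it conflicts with 12.3, which requires bypass for the same analysis. Section 12.10 lists all reported adverse events among the safety variables but names no safety population, so it does not override 5.1.1 and 12.4.

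**Step 3. Number of infants (assumed rates).** The inputs are 190 planned infants (section 12.1) and an assumed proportion r who are dosed but never reach bypass. The expected number is 190 × r. The chance of at least one is 1 − (1 − r)^190.

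- r = 0.5%: 0.95 infants expected; chance of at least one 61%
- r = 1%: 1.9 infants expected; chance 85%
- r = 2%: 3.8 infants expected; chance 98%

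One infant is 1/95 = 1.05 percentage points of an arm.

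**Step 4. What the safety table could show (assumed counts).** Suppose a harm that prevents bypass occurs in k of 95 MP infants, and all other infants reach bypass without it. The planned sample shows 0 of 95 − k. The upper limits below are from exact two-sided 95% intervals. For zero events the limit is 1 − 0.025^(1/(95 − k)).

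| k | Planned sample | Upper limit | All dosed infants | Upper limit |
|---|---|---|---|---|
| 1 | 0/94 | 3.85% | 1/95 | 5.73% |
| 3 | 0/92 | 3.93% | 3/95 | 8.95% |
| 5 | 0/90 | 4.02% | 5/95 | 11.86% |

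Under the planned rule the harm reads as zero at every k. The effect is on the description and the upper bound more than on a test: with no cases in 95 placebo infants, Fisher's exact p is 0.25 at k = 3 and 0.059 at k = 5.

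**The case against.** The other side has a good deal of substance.

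- **Early harms in general are not lost.** A reader might infer that everything in the first minutes after dosing is left out. The documents do not support that. An infant who reaches bypass is in the safety sample, and adverse-event collection for that infant began at receipt of drug.
- **One listed population does contain these infants.** A reader might infer that they appear in no analysis set at all. Section 12.9 has an all-randomized ITT set, although not for safety.
- **Follow-up and oversight are not absent.** A reader might infer that these infants vanish from view. Section 1.5.1 calls for follow-up after withdrawal for an adverse event, 6.1 lists only consent withdrawal as a reason for termination, and first-year deaths are reportable. All adverse events go to the semiannual DSMB meetings (10.1.1), and serious ones go to its chair within 72 hours of the PI's knowledge (10.2.4).
- **The direction of bias is unproven.** The rule applies to both blinded arms and would also remove placebo infants with line or anesthesia events. Nothing in the documents shows that a drug reaction is the likeliest reason for missing bypass. Known hypersensitivity is an exclusion, and 1.5.1 describes few side effects of a single dose.
- **The yield may be small.** The safety aim concerns the period after surgery, and the events named in 10.1.1 and 10.1.2 include no infusion reaction. Widening the sample would mainly add deaths. Dosing also comes just before planned surgery, so cancellations before the operating room are undosed.

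A collection window and an analysis population are different things, so 10.2.1 does not by itself contradict 12.4. The ending of participation in 5.1.1, however, does not sit with 1.5.1, 10.1.2 and 10.2.1. Reporting an event to the DSMB is also not the same as counting it in the final comparison by arm. Those two points stand.

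**Conclusion.** The concern holds in a narrow form. Infants who are dosed but never reach bypass are excluded from the MP-versus-placebo safety comparison by an event after exposure, and this includes any infant whose early harm is the reason bypass did not happen. The discontinuation rule in 5.1.1 must be reconciled with the collection, follow-up and death-reporting rules.

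The size rests on an assumed rate: about 1 to 4 of 190 infants at 0.5% to 2%, probably few, with no established direction of bias. The primary analysis and DSMB oversight are not at issue. This is a should-fix, not a must-fix.

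**What to change.** 1. In 5.1.1 and 12.4, define the safety sample as all randomized participants who received any amount of study drug, regardless of bypass, analysed by the drug received. Putting the same sentence in 12.10, which names no safety population, would keep the duplicate sections aligned.
2. In 5.1.1, state that discontinuation for lack of bypass does not end adverse-event and one-year vital-status data collection for an infant already dosed. This brings it into line with 1.5.1, 10.1.2 and 10.2.1.

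The efficacy sets stay as they are under this change. The cost is a few sentences of wording and chart follow-up of a few infants, with no added patients or study procedures.
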